8.1.1.1. American College of Rheumatology Response Criteria

The ACR criteria are standard criteria to measure the effectiveness of various arthritis medications or treatments in clinical trials. The ACR criteria were developed for rheumatoid arthritis but now are also frequently used for primary outcome measure in PsA clinical trials ([American College of Rheumatology, 2019](#)).

The ACR criteria are reported as percentage (%) improvement, comparing disease activity at 2 discrete timepoints (baseline and postbaseline comparison). The ACR criteria are indicated as:

- ACR20 is $\geq 20\%$ improvement
- ACR50 is $\geq 50\%$ improvement; ACR50 responders include ACR20 responders
- ACR 70% (ACR70) is $\geq 70\%$ improvement; ACR70 responders include ACR20 and ACR50 responders

The ACR20 criteria require that the subject experiences an improvement in the following parameters compared to baseline:

- $\geq 20\%$ reduction in TJC68 (see [Section 8.1.3.1](#))
- $\geq 20\%$ reduction in SJC66 (see [Section 8.1.3.1](#))
- $\geq 20\%$ reduction in 3 of 5 additional measures:
 - Subject's Assessment of Pain (see [Section 8.1.2.3](#))
 - Subject's Global Assessment of Disease Activity (see [Section 8.1.2.2](#))
 - Investigator's Global Assessment of Disease Activity (see [Section 8.1.3.2](#))
 - HAQ-DI (see [Section 8.1.2.6](#))
 - Acute phase reactant (C-reactive protein [CRP]).

Analyses of ACR50 and ACR70 include the same criteria as ACR20, with the use of a higher percentage improvement (50% and 70%, respectively) instead of 20% ([European Medicines Agency, 2007](#)).

The proportion of subjects achieving ACR20, ACR50, and ACR70 will be evaluated at Week 16.

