- Progression of structural damage assessed radiographically and expressed as the change in mTSS at Weeks 16 and 52, compared to baseline
- Change in SPARCC enthesitis score at Weeks 16, 24, and 52, as compared to baseline in subpopulation with enthesitis (SPARCC  $>0$ ) at baseline

- Change in spinal pain NRS at Weeks 16, 24, and 52, as compared to baseline in subjects reporting spinal pain at baseline
- Change from baseline in spine pain NRS in those with sacroiliitis on pelvic x-ray at Weeks 16, 24 and 52
- Change from baseline in spine pain NRS in those with investigator assessed spinal involvement at Weeks 16, 24 and 52
- Association of investigator assessed sacroiliac involvement with sacroiliitis on x-ray
- Proportion of subjects achieving each MDA component (TJC68, SJC66, PASI, BSA, SAPVAS, SGADA, HAQ-DI, tender enthesal points from LEI) at Weeks 16, 24 and 56
- Change in quality of life as assessed by SF-36 total score, physical component summary (PCS), and mental component summary (MCS) change from baseline to Weeks 16, 24, and 52
- Fatigue as assessed by FACIT-F change from baseline to Weeks 16, 24, and 52
- Proportion of subjects achieving ACR50 at Weeks 24 and 52
- Proportion of subjects with resolution of enthesitis at Weeks 24 and 52 as assessed by LEI in subpopulation that had enthesitis (LEI > 0) at baseline
- Proportion of subjects achieving an improvement in PsAID of at least 3 units at Weeks 24 and 52 compared to baseline in subjects with PsAID  $\geq 3$  at baseline
- Proportion of subjects achieving ACR20 at Weeks 24 and 52
- Mean (median) ACR-N at Week 16, where, ACR-N is defined as the largest number N such that ACR-N is met (analogous to the primary endpoint definition of ACR 50)
- Change in enthesitis at Weeks 16, 24 and 52 as assessed by change from baseline in LEI
- Time to resolution of enthesitis at weeks 4, 12 and 16 among subjects with enthesitis (LEI > 0) at baseline
- Occurrence of enthesitis (LEI > 0) at weeks 4, 12 and 16 among subjects without enthesitis (LEI = 0) at baseline
- Depression and anxiety as assessed by change in HADS score from baseline to Weeks 16 and 52
- Change in physical function as assessed by HAQ-DI change from baseline to Weeks 24 and 52
- Proportion of subjects with a decrease of at least 2 from baseline in LEI, among subjects with baseline LEI of at least 2, at weeks 4, 12 and 16
- Subject's Global Impression of Change Questionnaire at weeks 16 and 52

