## 5.2. Handling of Dropouts, Missing Data, and Outliers

### 5.2.1. Handling of Missing Efficacy Data

Tender (and swollen) joint count will be the sum of the joints where tenderness (or swelling) is marked as Present on the CRF. A missing response will be treated the same as an Absent response, in that, it will not contribute to the joint count.

Subjects with missing efficacy assessments will be imputed as non-responders (non-response imputation or NRI) for dichotomous endpoints. Subjects with a missing component of a composite endpoint will be imputed as non-responders for that component. The subject may therefore be a responder to the endpoint, if the subject met a sufficient number of criteria from other components.

Subjects missing one or more components of composite endpoints will be included, illustrated for the primary endpoint, ACR50, as follows:

Situation	ACR50 result
If both SJC66 and TJC68 have reductions $\geq 50\%$ : 
 
- If at least 3 of the other 5 components have reductions <math>\geq 50\%</math>, irrespective of missing/available on the others
 
- If at least 3 of the other 5 components have a reduction of <math>< 50\%</math>, irrespective of missing/available on the others
 
- All other situations
 
	
Responder
 
Non-responder
 
Missing

If result is available on both of SJC66 and TJC68, and at least one has $<50\%$ : 
 
- Irrespective of results or missingness on the other 5 components
 
	Non-responder
If one of SJC66 and TJC68 is missing, and the other has reduction $\geq 50\%$ : 
 
- If at least 3 of the other 5 components have reductions <math>\geq 50\%</math>, irrespective of missing/available on the others
 
- If at least 3 of the other 5 components have a reduction of <math>< 50\%</math>, irrespective of missing/available on the others
 
- All other situations
 
	
Missing
 
Non-responder
 
Missing

If one of SJC66 and TJC68 is missing, and the other has reduction $<50\%$ : 
 
- Irrespective of results or missingness on the other 5 components
 
	Non-responder

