If both SJC66 and TJC68 missing: 
 
- If at least 3 of the other 5 components have a reduction of <math>< 50\%</math>, irrespective of missing/available on the others
 
- All other situations
 
	
Non-responder
 
Missing

For continuous efficacy endpoints, inference will be done using mixed-effects models repeated-measures, which is robust to missing outcomes that are missing at random or missing complete at random.

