- Change from baseline in SF-36 total score, PCS, and MCS at Weeks 16, 24, and 52
- Change from baseline in FACIT-F at Weeks 16, 24, and 52
- Change from baseline in LEI enthesitis score at Weeks 16, 24, and 52 in those with enthesitis at baseline (LEI>0)
- HAQ-DI change from baseline to Weeks 24 and 52
- HADS change from baseline to Week 24 and 52

Change from baseline for the individual components of the ACR and MDA scores will be summarized at Week 16. Summary statistics (n, mean, standard deviation, median, minimum, and maximum) will be provided

- Swollen Joint Count
- Tender Joint Count
- SAPVAS
- SGADA
- IGADA
- HAQ-DI
- CRP
- PASI
- BSA
- Tender enthesal points  $\leq$  1 site out of 6 sites included in LEI

The following will be analyzed with a time to event model, using a log rank test with stratification by the factors used to stratify randomization. Subjects who do not achieve the endpoint at or before the week 16 visit will be censored at the time of the last assessment could be derived at or before week 16.

- Time to resolution of enthesitis (LEI = 0) among subjects with enthesitis (LEI = 0) at baseline.
- Time to first achievement of ACR50

- Time to first achievement of PASI90 among subjects with  $\geq 3\%$  BSA psoriasis at baseline
- Time to first achievement of MDA
- Time to first achievement of ACR20
- Time to first achievement of PsAID improvement of at least 3 among subjects with PsAID  $\geq 3$  at baseline
- Time to first achievement of PASI100 among subjects with PsAID  $\geq 3$  at baseline

WPI will be calculated at baseline. WPI is a scale of 0-19, and is a count of how many of 19 body sites the subject reports pain or tenderness in the prior 7 days. Standard summary statistics for binary data will be calculated by baseline WPI (WPI  $\geq 7$  vs.  $< 7$ ) for the following endpoints:

- ACR50 at week 16 (observed responder, observed non-responder, missing)
- LEI responders at week 16 (observed responder, observed non-responder, missing)
- PsAID at week 16 (observed responder, observed non-responder, missing)
- HAQ-DI at week 16: improvement of at least 0.35 (observed responder, observed non-responder, missing)

Area under the curve (AUC) for ACR-N will be calculated for each subject by triangulating the observed values at baseline (by definition ACR-N = 0 at baseline) and weeks 2, 4, 12 and 16. The area for consecutive visits, using nominal time from Week t and Week u, will be calculated as

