$$\text{AUC}_{\text{Week } t \text{ to Week } u} = ((u - t) \times (\text{ACR-N}_{\text{Week } t} + \text{ACR-N}_{\text{Week } u})/2$$

The AUC for the period through week 16 will be the sum of the individual values from week 0 through week 16. Any visits at which ACR-N cannot be calculated (including Week 0) will be imputed as ACR-N = 0. In case one or more components of ACR is missing, the smallest value N for which ACR-N is known to be achieved will be used.

Listings of all efficacy data, including derived composite values will be provided for the Full Analysis Set.

PK concentrations will be summarized by dose group and scheduled visit. Summary statistics reported will be number of samples, number of samples that are BLQ, arithmetic mean, standard deviation, coefficient of variation in percent (CV), minimum, median, maximum, geometric mean and the CV of the geometric mean in percent.

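### The SAP's missing-component rule for the ACR-N AUC takes the smallest N achieved where the definition of ACR-N requires the largest

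*SAP*

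**What the plan says.** SAP 2.2.3 defines the measure: "ACR-N is defined as the largest number N such that ACR-N is met". The Protocol gives the same definition in its Synopsis and in Section 3.

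SAP 6.6.5 builds the AUC by "triangulating the observed values at baseline (by definition ACR-N = 0 at baseline) and weeks 2, 4, 12 and 16", using the trapezoid formula on nominal weeks. Two rules for missing data follow in the same paragraph:

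- Whole visit: "Any visits at which ACR-N cannot be calculated (including Week 0) will be imputed as ACR-N = 0".
- One or more components missing: "the smallest value N for which ACR-N is known to be achieved will be used".

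Two other places bear on these rules. Protocol 8.1.1.1 states that the thresholds are nested: "ACR50 responders include ACR20 responders". SAP 5.2.1 gives the general rule for composites: "Subjects with a missing component of a composite endpoint will be imputed as non-responders for that component". It adds that such a subject may still be a responder on the other components, and its ACR50 table applies this.

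**The concern.** Because the thresholds are nested, anyone who meets ACR50 also meets every lower threshold. The smallest N known to be achieved is then the bottom of the scale for every subject: 0, or 1 if N must be a positive whole number. The observed components have no influence on it. The definition asks for the opposite end of the range.

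If the rule is programmed as written, a visit with a single missing measure is treated almost as if nothing had been observed. The loss is proportional to the subject's true ACR-N, so good responders lose most and non-responders lose almost nothing. The AUC is biased down. An izokibep-placebo difference would be attenuated even with equal missingness in the arms. The same dataset could also hold a subject who is an ACR50 responder at a visit and has ACR-N of 0 there.

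**Working it through.** The plan states no figure for the ACR-N AUC, so there is none to reproduce. The check applies the plan's formula.

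**Weights.** With visits at Weeks 0, 2, 4, 12 and 16, each interval contributes (u − t) × (ACR-N at t + ACR-N at u)/2. Collecting terms, each visit's weight is half the sum of its adjacent intervals:

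- Week 0: 2/2 = 1 (ACR-N is 0 here by definition)
- Week 2: (2 + 2)/2 = 2
- Week 4: (2 + 8)/2 = 5
- Week 12: (8 + 4)/2 = 6
- Week 16: 4/2 = 2

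**Loss from one affected visit.** Assume a subject steady at ACR-N 50 from Week 2. The complete-data AUC is 50 × (2 + 5 + 6 + 2) = 750. With ACR-N of 0 at one visit:

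| Visit affected | Loss | Share of 750 |
|---|---|---|
| Week 2 | 2 × 50 = 100 | 13% |
| Week 4 | 5 × 50 = 250 | 33% |
| Week 12 | 6 × 50 = 300 | 40% |
| Week 16 | 2 × 50 = 100 | 13% |

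**The two rules on one visit (assumed values).** ACR-N is the minimum of the TJC68 improvement, the SJC66 improvement and the third-largest improvement among the other five measures. Suppose CRP is missing and the improvements are TJC68 60%, SJC66 70%, pain 65%, subject's global 60%, investigator's global 62% and HAQ-DI 30%.

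- CRP counted as not improved: third largest of 65, 62, 60, 30 is 60, so ACR-N = min(60, 70, 60) = 60.
- CRP improved by 100%: third largest of 100, 65, 62, 60, 30 is 62, so ACR-N = min(60, 70, 62) = 60.

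ACR-N is 60 whatever CRP shows, and SAP 5.2.1 makes this subject an ACR50 responder. *Largest N known to be achieved* gives 60. *Smallest* gives 0.

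If this subject's ACR-N runs 0, 20, 40, 60, 60, the AUC is 2×20 + 5×40 + 6×60 + 2×60 = 720. The literal rule gives 720 − 360 = 360 (−50%) if CRP is missing at Week 12, and 720 − 120 = 600 (−16.7%) if at Week 16. The corrected rule leaves 720.

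**How much the corrected rule recovers.** A simulation used assumed inputs: mean improvement 20 or 45, SD 35, correlation 0.3 to 0.7 between components, and one of the five other measures missing. *Largest known* returned the complete-data ACR-N (floored at 0) in about 74% to 81% of cases and was 1.3 to 3.0 points low on average. The literal rule returned 0 every time.

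Recovery has a limit. Both joint counts are mandatory for any ACR response, so if TJC68 or SJC66 is missing, no positive N is known to be achieved and the value stays 0 under either wording.

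**Effect on an arm difference.** If a share m of values at every visit in both arms lacks a component, independently of response, the literal rule multiplies each arm's mean AUC, and so the difference, by (1 − m). Assume mean profiles of 0, 15, 25, 38, 40 (active) and 0, 6, 10, 14, 15 (placebo). The AUCs are 463 and 176, a difference of 287. That becomes 281 at m = 2%, 273 at 5% and 258 at 10%. The documents give no value for m.

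**The case against.** The strongest defence is that the intent can be read from the context. The preceding sentence already assigns 0 when ACR-N cannot be calculated, so a separate component rule does useful work only if it keeps partial information. The drafter may have meant the smallest value ACR-N could take given what was observed. That guaranteed lower bound is the same number as the largest N known to be met. This is probably right, and it makes the defect a slip of wording. It does not remove the defect, because the sentence attaches *smallest* to the N achieved, and a programmer has only the text.

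The defence is also right about scope. Individual missing joints count as absent under SAP 5.2.1 and do not make a joint count missing. Early-termination and unscheduled visits can be mapped to scheduled ones under SAP 5.1.4. Subjects with complete data are unaffected.

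A reader might go further in three ways that the documents do not support.

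- *The zero for visits at which ACR-N cannot be calculated is also an error.* It is explicit, and it parallels the plan's convention that "Subjects with missing efficacy assessments will be imputed as non-responders (non-response imputation or NRI) for dichotomous endpoints". At Week 0 it is true by definition. It differs from the general approach to continuous measures ("For continuous efficacy endpoints, inference will be done using mixed-effects models"), and it is costly for an intermittent gap at Week 4 or 12, but it is a conservative choice and contradicts nothing. Interpolation would credit response at an unobserved visit using later data, which is a preference.
- *The typical loss is 40%.* That is one subject at the heaviest visit.
- *The Week 16 ACR-N endpoint is distorted too.* Both rules sit in the AUC paragraph, and the SAP does not say that they apply elsewhere.

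**Conclusion.** The component rule is wrong as written. It contradicts the definition of ACR-N in both documents and the composite rule in SAP 5.2.1. Followed literally, it reduces ACR-N to about 0 at any visit with a missing component.

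For a subject steady at ACR-N 50, the cost per affected visit is 13% to 40% of the AUC, depending on the visit. These are illustrations for single subjects. The bias in group means depends on missing-component rates, which the documents do not give, and the range shown for an arm difference assumes missingness unrelated to response and equal in the arms.

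Consequences are limited. Exploratory p-values are descriptive under SAP 6.6.5, and no primary or secondary test and no sample-size calculation uses this AUC. The correction matters only for subjects with a gap among the five measures other than the joint counts.

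**What to change.** In the missing-component sentence of SAP 6.6.5, replace *smallest* with *largest*. Add a clause saying that missing components count as not improved, in line with SAP 5.2.1, so that the value is 0 when TJC68 or SJC66 is missing. The cost is one word and one clause, with no new data or analyses.

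It would help to say in the same edit whether the rule also governs ACR-N at Week 16. The zero rule for visits at which ACR-N cannot be calculated can stay. Linear interpolation between observed visits is at most an optional sensitivity analysis.

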### 6.6.6. Subgroup Analysis

Various subgroup analyses of the efficacy data will be reported. These analyses will investigate the treatment response within specific subgroups of interest, and assess whether the treatment response is consistent across different subgroup levels. All analyses will be performed on the FAS data set. Treatment effect will be summarized by comparison (QW versus placebo; Q2W versus placebo) and presented in tables and a forest plot.

Summaries of primary and secondary efficacy endpoints will be presented by subgroup:

The following subgroups are of interest for the primary and all secondary endpoints:

- Race (Asian, White, Black or African American, other)
- Sex (male, female)
- Age (< 65, ≥ 65)
- Prior TNFi use (Yes/No)

The following subgroups are also of interest for ACR50 at Week 16 and all secondary endpoints:

- Any csDMARD at Baseline (Yes/No)
  - MTX only
  - MTX + other csDMARD
  - Non-MTX csDMARD only
  - No csDMARD at baseline
- Any prior TNFi exposure (Yes/No)
- Prior TNFi failure (Yes/No)
- Number of prior failed biologics group (0, 1, 2 or more)
- Geographic region
  - North America (US or Canada)
  - Europe (Bulgaria, Czech Republic, Spain, Hungary, Poland or Germany)
  - Non-US (Bulgaria, Czech Republic, Spain, Hungary, Poland, Germany or Canada)
- Country
  - United States
  - Canada
  - Bulgaria
  - Czech Republic
  - Poland
  - Hungary
  - Spain
  - Germany
- BMI ( $\leq 18$ ,  $> 18 - \leq 25$ ,  $> 25 - \leq 30$ ,  $> 30 - \leq 35$ ,  $> 35$ )
- Smoking status (never, former, current)

- Enthesitis at baseline
  - LEI = 0
  - LEI > 0
  - LEI = 1
  - LEI = 2
  - LEI = 1 or 2
  - LEI < 3
  - LEI  $\geq$  3
  - LEI < 4
  - LEI  $\geq$  4
- Combination of enthesitis and prior TNFi exposure
  - LEI = 1 or 2 and no prior TNFi exposure
  - LEI  $\geq$  3 and no prior TNFi exposure
  - LEI = 1 or 2 and prior TNFi exposure
  - LEI  $\geq$  3 and prior TNFi exposure

The following endpoints are of interest for the subjects with enthesitis at baseline (LEI > 0) and subjects without enthesitis (LEI = 0) at baseline:

- PsAID response at Week 16
- PsAID change from baseline to Week 16
- HAQ-DI response at Week 16
- HAQ-DI change from baseline to Week 16
- Change in DAPSA and cDAPSA from baseline to Week 16
- VLDA at Week 16
- Change in SF-36 total score, physical component summary (PCS), and mental component summary (MCS) from baseline to Week 16
- MDA at Week 16 (including each component of MDA)

The following subgroups are of interest for summarizing Time to resolution of enthesitis (LEI = 0) among subjects with enthesitis (LEI = 0) at baseline.

- Sex (male, female)
- Prior exposure to TNFi (yes, no)
- LEI score at baseline
  - LEI = 1
  - LEI = 2
  - LEI = 1 or 2
  - LEI  $\geq$  3

The following subgroup is of interest for the endpoints of PASI75, PASI90 and PASI100:

- Baseline BSA 10% or greater

Response rates and difference in response rate will be reported for each subgroup. Cochran-Mantel-Haenszel weighting will be used to calculate a 95% CI for subgroup analyses for each endpoint similar to Section 6.6.1 and 6.6.3 using stratified tests. A forest plot for the difference in response rate and 2-sided 95% CI will also be presented. No p-values will be reported for the subgroup analyses.

PsAID and HAQ-DI response rates will be determined by the proportion of subjects who achieve at least a minimum clinically important difference (MCID) improvement from baseline to Week 16. MCID values are 3 units for PsAID and 0.35 units for HAQ-DI.

Similar to the subgroup analysis above, difference in response rate and 2-sided Cochran-Mantel-Haenszel weighted stratified 95% CI will be reported for subgroup analyses for each binary endpoint.

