9.3. Statistical Analyses

9.3.1. General Considerations

All data collected will be summarized by planned timepoint without imputation. Continuous data will be summarized with count, mean, Q1, median, Q3, standard deviation, minimum, and maximum. Change from baseline will additionally include standard error. Categorical data will be summarized with count and percent. Time to event data will be summarized with product-limit estimators of median and quartiles.

All hypothesis tests will be reported with 2-sided *p*-values. Comparison of QW dosing to placebo will use only subjects assigned to receive izokibep 160 mg QW or placebo; comparison of Q2W dosing to placebo will use only subjects assigned to receive izokibep 160 mg Q2W or placebo; comparison of Q4W izokibep to placebo will use only subjects assigned to receive izokibep 80 mg Q4W or placebo. All confidence intervals will be 2-sided with nominal 95% coverage.

Data will be summarized by planned timepoint, using data collected at the visit. Study day will be calculated as postbaseline date minus randomization date, plus 1 (except that study day for pre-randomization dates will not include the plus 1). Day range windows will not be applied for summaries (but may be applied for protocol deviations). Baseline values will be the last value collected before randomization and change from baseline will be calculated as postbaseline value minus baseline value.

Stratified tests will use the strata of prior TNFi use (Yes/No) and enthesitis at baseline (LEI = 0 versus > 0) from the randomization process. If a subject is incorrectly classified into a stratum during the randomization process, the analysis will use the correct classification, not the classification used during randomization.

Primary and secondary endpoints will be tested using only three treatment groups: izokibep 160 mg Q2W, izokibep 160 mg QW and placebo. The treatment group receiving izokibep 80 mg Q4W will only be used for exploratory analyses and endpoints.

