### **3.1.5. Population-level Summary for Comparison between Treatment Conditions**

The population level summary is the response rate, or proportion of subjects who meet ACR50 at Week 16. The null hypothesis of equal response rates will compare each dosing regimen of izokibep to the placebo group respectively. A stratified test of response rates will be implemented in the analysis. Stratified tests will use the strata of prior TNFi use (Yes/No) and enthesitis at baseline (LEI = 0 versus  $>0$ ) from the randomization process. If a subject is incorrectly classified into a stratum during the randomization process, the analysis will use the correct classification, not the classification used during randomization. Within each of the strata used for randomization, the response rate for each treatment group and corresponding standard error will be calculated. The difference in response rates (risk difference) will be calculated for each stratum. The common risk difference among the strata and associated standard error will be estimated by combining the observed risk differences using Cochran-Mantel-Haenszel weighting. The estimated risk difference divided by the standard error will be used as the test statistic and a p-value calculated assuming that the test statistic follows a standard normal distribution under the null hypothesis. Analyses at earlier timepoints when data to calculate the ACR50 are collected will also be presented using the same methodology. P-values from earlier timepoints will be presented for descriptive purposes, not part of the alpha-preserving multiple testing strategy.

The treatment effect will be quantified by the response rate difference of ACR50 at Week 16 between placebo and each dosing regimen of izokibep at Week 16.

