The null hypothesis of equal response rates will compare each dosing regimen of izokibep to the placebo group. A stratified test of response rates will be used. Within each of the strata used for randomization, the response rate for each treatment group and corresponding standard error will be calculated. If a subject is incorrectly classified into a stratum during the randomization process, the analysis will use the correct classification, not the classification used during randomization. The difference in response rates (risk difference) will be calculated for each stratum. The common risk difference among the strata and associated standard error will be estimated by combining the observed risk differences using Cochran-Mantel-Haenszel weighting. The estimated risk difference divided by the standard error will be used as the test statistic and a p-value calculated assuming that the test statistic follows a standard normal distribution under the null hypothesis. A confidence interval on the difference will be calculated using analogous methods. Analyses at earlier timepoints when data to calculate the ACR50 are collected will also be presented using the same methodology. P-values from earlier timepoints will be presented for descriptive purposes, not part of the alpha-preserving multiple testing strategy.

The number and proportion of subjects achieving ACR50 in each treatment group will be reported at each scheduled assessment, along with Clopper-Pearson 95% CI without strata. The common risk difference with Cochran-Mantel-Haenszel weighting will be used to calculate a 95% CI for difference in response rates. A bar graph showing the proportion of subjects achieving ACR50 for each treatment group along with the associated p-value will be produced. ACR50 results will also be listed.

Sample SAS code with stratification factors of comparing each dosing regimen of izokibep to the combined placebo group is given as following:

```
ods output commonpdif = ;
proc freq data= ;
  tables stratum * treatment * response / cmh commonriskdiff (test=mh cl=mh);
  weight count / zeros;
run;
```

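### SAP 6.6.6 applies a large-sample stratified Mantel-Haenszel 95% interval to every subgroup level with no minimum size; in small levels it covers clearly less than 95%

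*SAP*

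**What the plan says.** SAP 6.6.6 lists the subgroups for the primary and secondary endpoints. They include eight countries, five BMI classes (one of them 18 or below), several LEI classes, combinations of LEI and prior TNFi exposure, and race, given as "Race (Asian, White, Black or African American, other". Each active regimen is compared with placebo separately, and the results go into tables and a forest plot whose stated purpose is to show whether the effect is consistent across levels.

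The interval method is given twice in that section: "Cochran-Mantel-Haenszel weighting will be used to calculate a 95% CI for subgroup analyses for each endpoint", and again, "2-sided Cochran-Mantel-Haenszel weighted stratified 95% CI will be reported for subgroup analyses for each binary endpoint". It is tied to SAP 6.6.1, whose sample code contains "tables stratum * treatment * response / cmh commonriskdiff (test=mh cl=mh". The text of 6.6.1 describes the variance differently: "Within each of the strata used for randomization, the response rate for each treatment group and corresponding standard error will be calculated", with the stratum differences then combined by Cochran-Mantel-Haenszel weights. SAP 3.1.5 defines the strata: "Stratified tests will use the strata of prior TNFi use (Yes/No) and enthesitis at baseline", which makes four. Protocol 9.3.1 adds: "All confidence intervals will be 2-sided with nominal 95% coverage".

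Neither document sets a smallest subgroup level for which the interval is reported, a rule for pooling sparse strata, or an alternative interval for small samples. Neither gives an expected size for any country, race or BMI class.

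**The concern.** The Mantel-Haenszel interval rests on a large-sample approximation. That is sound for 100 against 100. In a level with only a few subjects per arm, two things go wrong:

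- The normal approximation gives intervals that are too short.
- A stratum with subjects in one arm only receives weight zero. Its subjects drop out of the stratified difference but remain in the displayed response rates, so the plotted difference need not agree with the rates beside it.

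At stake is how the forest plot is read. An interval labelled 95% that covers 80% makes chance variation between countries or races look like real inconsistency, and occasionally the interval has no width at all.

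**Working it through.** **Inputs**

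- ACR50 rates of 20% (placebo) and 45% (izokibep), 100 per arm: SAP 2.3.
- Prior TNFi use 20% to 30%: SAP 2.1. The value used is 25%.
- LEI > 0: up to 60% (SAP 2.3) and at least 30%, because LEI = 0 is capped at 70% (SAP 2.1). The value used is 50%.
- Assuming the two factors are independent, the four strata have shares 0.125, 0.125, 0.375 and 0.375.
- Subgroup size per arm: not in the documents, so varied from 4 to 20.

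**The plan's own figure.** With 100 per arm the pooled SE is √(2 × 0.325 × 0.675/100) = 0.0662 and the unpooled SE is √((0.20 × 0.80 + 0.45 × 0.55)/100) = 0.0638. Then (0.25 − 1.96 × 0.0662)/0.0638 = 1.88, a power of 97%, as stated. The documents give no coverage figure other than the nominal 95%.

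**Plausible sizes**

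- Countries: 100/8 = 12.5 per arm on average. Any imbalance puts at least one country below that.
- Enthesitis resolution (LEI > 0 only): SAP 2.3 considers 50 or 30 per arm, so 50/8 = 6.3 or 30/8 = 3.8 per arm per country.
- LEI ≥ 1 with prior TNFi exposure: between 100 × 0.20 × 0.30 = 6 and 100 × 0.30 × 0.60 = 18 per arm (independence assumed), shared between the two LEI classes listed.

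**Formulas.** In stratum k, let n1, n0 be the arm sizes, x1, x0 the responders, and N = n1 + n0.

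- Weight: w = n1·n0/N. With n1 = 3 and n0 = 0, w = 0.
- Difference: d = Σ[(x1·n0 − x0·n1)/N] / Σw.
- Variance for "commonriskdiff (test=mh cl=mh" (Sato): [d·ΣP + ΣQ]/(Σw)², where P = [n1²·x0 − n0²·x1 + n1·n0·(n0 − n1)/2]/N² and Q = [x1(n0 − x0) + x0(n1 − x1)]/(2N).
- Interval: d ± 1.96·SE.

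If the contributing strata contain no responders in either arm, then d = 0 and Q = 0, and the interval has zero width.

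**Simulation** (60,000 samples per size, equal arms, true difference 25 points in every stratum)

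| Per arm | MH, code variance | MH, per-stratum SEs | Unstratified Wald | Unstratified Newcombe | A stratum drops | Subjects lost |
|---|---|---|---|---|---|---|
| 4 | 63% | 46% | 79% | 96% | 84% | 26% |
| 6 | 81% | 69% | 88% | 94% | 80% | 16% |
| 8 | 88% | 78% | 92% | 95% | 73% | 10% |
| 12 | 91% | 86% | 91% | 95% | 56% | 5% |
| 20 | 93% | 90% | 94% | 95% | 24% | 2% |

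At 4 per arm about 2% of samples give no estimate (the 63% is among the rest), and about one sample in five gives an interval of zero width. At 8 per arm the stratified difference departs from the difference of the displayed rates by more than 10 points in 31% of samples; at 12 per arm, in 15%. At 100 per arm coverage with the code variance is 95%, so the shortfall is a matter of size.

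**Sensitivity.** With random rather than equal allocation inside the level, coverage with the code variance is 78% at 12 subjects in both arms together, 86% at 16 and 91% at 25. In those runs, moving prior TNFi over 20% to 30% and LEI > 0 over 30% to 60% leaves coverage at 20 subjects in total at 89%. For enthesitis resolution at 25% versus 60%, where only the two TNFi strata remain, coverage is 83% at 4 per arm and 87% at 6.

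**The case against.** **Scope.** A reader might infer that the intervals for every country, race and BMI class fall far below 95%. The documents do not support that. At 12 per arm, close to an equal split over eight countries, coverage is 91%, and at 20 it is 93%. No section gives the sizes that would place a named level at 4 to 8 per arm. This stands.

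**Cause.** A reader might also put the whole shortfall down to dropped strata. The unstratified Wald interval has none to drop and still covers only 79%, 88%, 92% and 91% at 4, 6, 8 and 12 per arm. At 12 it matches the stratified interval although a stratum drops in 56% of samples. Empty strata add materially only at about 8 or fewer per arm. This stands too.

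**Strata and endpoints.** Four strata do not apply everywhere. Prior-TNFi and LEI subgroups keep two, and their combinations keep one. Enthesitis resolution has at most two in any country. HAQ-DI change uses a repeated-measures model, so Mantel-Haenszel weighting plays no part.

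**Impact.** Subgroups carry no p-values and lie outside the testing sequence. Median interval width is about 88 points at 8 per arm and 73 at 12, so a reader will see that the estimate is imprecise. Pooled regions are planned as well, and 6.6.1 provides Clopper-Pearson intervals for the arm-level rates. A display rule for small cells could also sit in the table shells that SAP 6.1 refers to, which are not available here. These points lower the impact. They do not remove the problem, because the SAP text as written prescribes this interval for every level, and the forest plot of differences is how consistency is to be shown.

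**Conclusion.** The point holds for small subgroup levels of binary endpoints. With the SAP's code and its ACR50 assumptions, nominal 95% intervals cover about 63% to 88% at 4 to 8 per arm, 91% at 12 and 93% at 20. With the per-stratum standard errors described in the text, coverage is lower at each size. Both the normal approximation and, in the smallest levels, zero-weight strata contribute.

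The result rests on assumed subgroup sizes, a common 25-point difference, and stratum shares taken from the planned ranges. Small levels are plausible, given an average of 12.5 per arm per country and about 4 to 6 for enthesitis resolution, but the documents do not show which levels they will be. It would be wrong to read this as a flaw in the primary or secondary tests: these use about 100 per arm, or the planned 30 to 50 with enthesitis, and their place in the alpha-controlled sequence is untouched. The consequence is confined to descriptive displays, but it is worth correcting because the correction is cheap.

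**What to change.** Add a rule to SAP 6.6.6. For any subgroup level with fewer than a prespecified number of subjects in either arm of a comparison, counted in that endpoint's analysis population, report the unstratified risk difference with a Newcombe 95% interval. Twenty per arm is a reasonable threshold, since the stratified interval covers about 93% there; the exact value is a judgement. Footnote these rows in the forest plot, and keep the stratified method for larger levels.

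The cost is a few lines of SAP text and code. Small levels lose the stratification, and the plot mixes two interval methods. The method for one level may also differ between the QW and Q2W comparisons or between endpoints, which the footnote should make visible. Suppressing the interval below a stated size would be simpler, but it shows the reader less.
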